This trial is for patients with resected pancreatic adenocarcinoma who have concluded adjuvant therapy or were deemed unable to receive adjuvant therapy with an elevated CA 19-9 or node positive or margin positive disease. CA 19-9 elevation is defined as two levels > the institutional upper limit of normal (ULN) taken at least 2 weeks apart. These levels should be measured after adjuvant therapy has concluded or upon the decision that adjuvant therapy will not be offered. Patients will be randomized to one of two arms. Subjects enrolled due to node + disease or R1 resection must be able to undergo randomization within 3 months of finishing adjuvant therapy or the decision that they are unable to take adjuvant therapy has completed. Group A, the treatment arm, will be started on CC-486. Group B, the control arm, will receive no additional therapy. In both arms, CA 19-9 will be followed and CT scans (or MRI, if clinically indicated) will be done every three months. When patients have visible disease recurrence on imaging, CC-486 will be stopped and both groups will start first-line chemotherapy.

Assuming the maximum accrual with a goal of 2-3 subjects accrued per month, we estimate enrollment duration of 24 months with an additional 12 months for follow-up with concurrent data analysis and manuscript preparation.

TOTAL SAMPLE SIZE:

Maximum 60 patients, with 30 patients in each of the two arms.

[figure not shown]
DRUG SUPPLIES:

For study participants, Celgene Corporation will provide CC-486

DOSING REGIMEN:

Treatment Arm	DRUG	DOSE	FREQUENCY	# of CYCLES	Route
Α	CC-486	300 mg total, three 100 mg tablets	Daily, Days 1- 21, Q28 Day cycles	12 cycles and then follow-up	Oral
В	Observation	N/A	N/A	12 cycles. Follow-up 1 will be collected 3 months after Cycle 10.	N/A

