11.3.4 Sample Size

The anecdotal time to progression without treatment is approximately 4 to 6 months. A feasible goal of 60 patients (30 in each arm) will provide 80% power to identify a 64% improvement in the median PFS from the null rate of 6 months assuming a one-sided type 1 error rate of 0.20, 24 months of accrual and a minimum of 12 months of follow-up while allowing for 10% loss to follow-up (protocol accruing for 6 months at the time of submission.

1-sided Type I error rate	Detectable HR (N = 60)
0.05	2.12
0.10	1.89
0.15	1.74
0.20	1.64

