11.3.5 Safety Monitoring

Although the dose level is below the maximally tolerated dose, we will monitory the rates of grade 3/4 toxicity for individuals treated with CC-486. We would expect to observe grade 3/4 toxicities in 15% of patients. The goal is to ensure that the percentage of grade 3/4 toxicities remains below 30%. A Bayesian stopping guideline has been developed. The prior was chosen to be a Beta (1, 4), representing a 20% toxicity rate, which is at the high end of our expected value. The guidelines will recommend that the therapy be re-evaluated if the posterior probability of toxicity exceeding 30% is greater than 65%. Table 11.3.5.1 below summarizes the stopping guideline boundaries.

Table 11.3.5.1

Cohort size	Observed number of toxicities that trigger re-evaluation
6-9	4
10-12	5
13-15	6
16-18	7
19-21	8
22-24	9
25-27	10
28-31	11

The probability of triggering the stopping guidelines was assessed for a range of underlying toxicity rates based upon simulations with 5000 replicates (Table 11.3.5.2 below). In the expected range of toxicity, the probability of stopping early was less than 4.8%.

Table 11.3.5.2

True underlying toxicity rate	Probability of triggering stopping guideline boundaries
10%	1.2%
15%	4.8%
20%	14.1%
25%	32.2%
30%	54.1%
40%	89.6%
50%	99.1%

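### Table 11.3.5.2 overstates how often the toxicity guideline would trigger: with 30 Arm A patients the rule reaches at most 29.4/49.0/83.7/97.7% at true rates of 25/30/40/50%, not 32.2/54.1/89.6/99.1%.

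*Combined protocol and SAP*

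**What the plan says.** Section 11.3.5 monitors "rates of grade 3/4 toxicity for individuals treated with CC-486", that is, Arm A only. The expected rate is 15%, and the aim is to keep the rate below 30%.

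- **Prior:** "The prior was chosen to be a Beta (1, 4), representing a 20% toxicity rate".
- **Rule:** "The guidelines will recommend that the therapy be re-evaluated if the posterior probability of toxicity exceeding 30% is greater than 65" per cent.
- **Boundaries (Table 11.3.5.1, cohort size: toxicities):** 6–9: 4; 10–12: 5; 13–15: 6; 16–18: 7; 19–21: 8; 22–24: 9; 25–27: 10; 28–31: 11.
- **Operating characteristics (Table 11.3.5.2):** "The probability of triggering the stopping guidelines was assessed for a range of underlying toxicity rates based upon simulations with 5000 replicates". The probabilities are 1.2, 4.8, 14.1, 32.2, 54.1, 89.6 and 99.1% at true rates of 10, 15, 20, 25, 30, 40 and 50%. The text adds that early stopping in the expected range has probability below 4.8%.

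The size of Arm A is given twice: "Maximum 60 patients, with 30 patients in each of the two arms" in Section 1.1, and "A feasible goal of 60 patients (30 in each arm) will provide 80% power" in Section 11.3.4. The plan states neither the maximum number of patients used in the simulation nor the look schedule.

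**The concern.** Table 11.3.5.2 is the plan's only statement of how well the guideline detects excess toxicity. An ethics board or safety committee would use it to judge whether the rule is good enough. The prior, cut-off, boundaries and arm size are all given, so the table can be checked exactly. The upper four rows look too high for a 30-patient arm.

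Those rows are the ones that matter most, because they cover true rates close to or above the 30% the guideline is meant to guard against. All four discrepancies make the rule look more sensitive than it is.

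**Working it through.** **1. Boundaries.** With x toxicities in n patients the posterior is Beta(1 + x, 4 + n − x). The boundary at n is the smallest x for which P(rate > 0.30) exceeds 0.65. Examples:

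- n = 6: x = 3 gives 0.6496 (no trigger) and x = 4 gives 0.8497, so the boundary is 4.
- n = 30: x = 10 gives 0.5545 and x = 11 gives 0.6932, so the boundary is 11.

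Done for every n from 6 to 31, this reproduces Table 11.3.5.1 throughout, so the rule has been read as intended.

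**2. Trigger probability.** Let f(n, k) be the probability of k toxicities among n patients with no trigger so far, and p the true rate:

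f(n, k) = (1 − p) · f(n − 1, k) + p · f(n − 1, k − 1)

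At each look, all probability with k at or above the boundary is removed and counted as triggered. The total removed by n = N is the trigger probability. It is exact, with no simulation.

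**3. Result at N = 30, looking after every patient from n = 6.** The Monte Carlo standard error is √[q(1 − q)/5000], with q the exact probability.

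| True rate | Stated (%) | Exact (%) | Difference (points) | SE (points) | Difference in SEs |
|---|---|---|---|---|---|
| 10% | 1.2 | 1.07 | 0.1 | 0.15 | 0.9 |
| 15% | 4.8 | 4.96 | −0.2 | 0.31 | −0.5 |
| 20% | 14.1 | 14.06 | 0.0 | 0.49 | 0.1 |
| 25% | 32.2 | 29.37 | 2.8 | 0.64 | 4.4 |
| 30% | 54.1 | 48.97 | 5.1 | 0.71 | 7.3 |
| 40% | 89.6 | 83.68 | 5.9 | 0.52 | 11.3 |
| 50% | 99.1 | 97.65 | 1.4 | 0.21 | 6.8 |

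The first three rows are reproduced. The last four are not.

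**4. Look schedule.** Removing a look can only remove triggers, so looking after every patient is the ceiling for these boundaries. Looks at 6, 9, ..., 30 give identical values: they fall at the last cohort size of each boundary row, and the count cannot fall within a row. Sparser looks give less. For example, looks at 6, 12, 18, 24 and 30 give 24.6, 44.0, 81.2 and 97.2% at true rates of 25, 30, 40 and 50%.

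**5. Other readings of the plan.**

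| Reading | 10% | 15% | 20% | 25% | 30% | 40% | 50% |
|---|---|---|---|---|---|---|---|
| Stated | 1.2 | 4.8 | 14.1 | 32.2 | 54.1 | 89.6 | 99.1 |
| N = 31 (end of Table 11.3.5.1), from n = 6 | 1.1 | 5.0 | 14.3 | 30.1 | 50.4 | 85.2 | 98.1 |
| N = 30, posterior rule from patient 1 | 2.3 | 7.3 | 17.2 | 32.6 | 51.7 | 84.7 | 97.8 |
| N = 40, from n = 6 | 1.1 | 5.0 | 14.8 | 32.0 | 54.3 | 89.5 | 99.2 |

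N = 31 is still short in the upper four rows. Starting at patient 1, where Table 11.3.5.1 has no boundary, fits the 25% row. It overshoots the three low rows and still falls short at 30, 40 and 50%. N = 40 fits every row to within 0.7 points, but the documents nowhere mention 40 treated patients.

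**6. Missed signals.** At a true rate of 40%, the chance of never triggering is at least 100 − 83.7 = 16.3%, against 100 − 89.6 = 10.4% implied by the table. The ratio is 16.3/10.4, or about 1.6.

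**The case against.** The strongest reply concerns weight and framing, not the arithmetic.

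- **Materiality.** The boundaries are right, so nothing done to patients changes. The rows at the expected rate (15%) and the prior mean (20%) hold, so the false-alarm rate is sound. The broad reading also survives: near even odds at 30%, strong detection at 40%, near certainty at 50%. A count of standard errors shows that the figures are not reproducible, not that the gap is important, and 1.4 points at 50% has no practical weight. All of this stands and limits the severity.
- **Other safeguards.** The guideline prompts a re-evaluation and is not an automatic stop. Patient-level dose rules (Sections 5.3.2 and 5.4), Safety Monitoring Committee oversight (10.3) and monthly safety calls (10.5) also apply. This too stands: the table is the only description of the guideline's performance, not the only protection.
- **Perhaps a sound simulation at another N.** The close match at N = 40 makes this plausible, but it is inference. It would not rescue the table, because Sections 1.1 and 11.3.4 fix the arm at 30 and Table 11.3.5.1 ends at 31.
- **The prose rule gives no starting patient.** The ceiling therefore applies to the tabled boundaries, which begin at 6. Starting earlier does not reproduce the table either (step 5).

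**Conclusion.** The concern holds. For the 30 planned Arm A patients, the last four rows of Table 11.3.5.2 are too high by at least 2.8, 5.1, 5.9 and 1.4 points, well beyond simulation error. At a true rate of 30% the guideline triggers slightly less than half the time (49.0%), not 54.1%.

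This rests on three things: the boundaries as tabled from n = 6, independent patients with a common toxicity rate, and a maximum of 30 treated patients. It does not depend on the look schedule. The rows for 10, 15 and 20% and the whole of Table 11.3.5.1 are not in dispute. This is a correction to reported operating characteristics that should be made; it does not call for a change of design.

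**What to change.** 1. Rerun Table 11.3.5.2 with a maximum of 30 treated patients and replace it. With looks after every patient from n = 6, or every third patient from n = 6, the rows become 1.1, 5.0, 14.1, 29.4, 49.0, 83.7 and 97.7%.
2. State the maximum number of patients and the look schedule. If another schedule is intended, name it and report its own values. If a larger N was simulated on purpose, say so and reconcile it with Sections 1.1 and 11.3.4.
3. Change the adjacent sentence on early stopping in the expected range from below 4.8% to about 5.0%.
4. Leave Table 11.3.5.1 as it is.

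The cost is one rerun, one replaced table, one added sentence and one edited sentence. The reported performance becomes slightly less favourable; boundaries and conduct are unaffected.

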11.3.6 Futility Analysis

An interim futility analysis will be performed once 50% of the expected progressions have occurred. The conditional power will be calculated for the following three scenarios for the unobserved data:

• Null hypothesis: Assumes no difference between the two treatment arms, i.e. the median PFS in both groups is 6 months.

- Alternative hypothesis: Assumes that the originally hypothesized rates (6 months vs 9.84 months) will be observed.
- Current pattern: Assumes that the PFS observed for each group in the initial cohort will be observed for the remaining patients.

The decision to stop or continue will be based upon the currently observed pattern with the null and alternative hypothesis patterns providing an estimate of the range of possible values. Since the cost of continuing (in terms of safety, resources and monetary cost) is low relative to the information to be gained, a low threshold for continuing was selected. We will stop the trial and conclude futility if the conditional power is 30% or less. Otherwise, the trial will continue. No interim efficacy analysis is planned due to the high cost of type I error spending associated with an interim efficacy analysis.

12 Regulatory Considerations

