11.3 Statistical Methodology

11.3.1 Efficacy Analyses

Progression free survival is defined as the time from randomization until visible recurrence on any imaging modality, a confirmed biopsy, or death. Individuals lost to follow-up prior to having an event will be censored at the time of the last scan or biopsy. In the case of an equivocal scan reading, the patient will be re-imaged on schedule, if clinically appropriate, and if subsequent reimaging confirms recurrence, the event will be considered to have occurred at the first time point when a related abnormality was noted. Overall survival is defined as the time from enrollment until death. Individuals lost to follow-up prior to death will be censored at the time of last physician contact.

Time to event outcomes, including the primary endpoint progression free survival and overall survival, will be summarized using Kaplan-Meier estimates of the survival function. From these estimates, median time to event and one-year survival proportions with 95% confidence intervals will be extracted. Cox proportional hazards models will be used to compare the two treatment arms and to evaluate and adjust for potential prognostic factors (e.g. nodal status, microscopic margins, increase in CA19-9, therapy). The number and type of responses to chemotherapy will be tabulated for each group. Logistic regression will be used to compare the response rate between the groups and to identify risk factors associated with response. Results will be considered statistically significant for p-values < 0.05.

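### The 80% power in 11.3.4 ignores the firm futility stop in 11.3.6; with the stop counted, power is about 72% against the one-sided 0.20 test, and the rule's stopping probabilities are not reported

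*Combined protocol and SAP*

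**What the plan says.** Section 11.3.4 makes the following claim for 60 patients split equally between the two groups: "will provide 80% power to identify a 64% improvement in the median PFS from the null rate of 6 months". The significance level behind that claim is given as "assuming a one-sided type 1 error rate of 0.20". Accrual is to run for 24 months, every patient is to be followed for at least 12, and the calculation is made "while allowing for 10% loss to follow-up". The section mentions no interim look.

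Section 11.3.6 adds one: "An interim futility analysis will be performed once 50% of the expected progressions have occurred". Conditional power is to be calculated under three scenarios, but only one drives the decision: "The decision to stop or continue will be based upon the currently observed pattern". The null and alternative scenarios serve only to show a range. The rule itself reads: "We will stop the trial and conclude futility if the conditional power is 30% or less". In any other case the study goes on. There is no interim test for efficacy.

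Section 11.3.1 covers the final comparison: "Cox proportional hazards models will be used to compare the two treatment arms". It ends with a general criterion: "Results will be considered statistically significant for p-values < 0.05".

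**The concern.** A futility rule that is obeyed can only lower power, because some trials that would have succeeded at the end are stopped at the look. The rule in 11.3.6 is worded as a commitment, and nothing elsewhere makes it advisory. The plan does not count what the rule costs, does not say how often it would stop the trial under either hypothesis, and does not give the expected number of progressions that fixes the timing of the look. By contrast, 11.3.5 tabulates simulated triggering probabilities for the safety guideline.

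The rule also lacks an input. Conditional power is the chance of passing a particular final test, and 11.3.6 names none. Section 11.3.4 points to one-sided 0.20; 11.3.1 mentions only p < 0.05. The same interim data could stop the trial under one reading and continue it under the other.

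At stake is the chance of discarding a drug that has the effect the trial was designed to find, and a reader's ability to interpret a futility stop.

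**Working it through.** **Inputs.** From 11.3.4: 60 patients, 1:1; median PFS 6 months in control; ratio 1.64, so 9.84 months in the treated arm (also given in 11.3.6); one-sided 0.20; 24 months' accrual; 12 months' minimum follow-up; 10% loss. From 11.3.6: look at information fraction t = 0.5; observed-trend conditional power; stop at 30% or less. Assumptions not in the plan: exponential PFS, uniform accrual, and the 10% loss taken as 54 evaluable patients. Hazard ratios are control over treated, as in the plan's table.

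**1. Expected events.** With λ = ln 2 / median, the probability of an event by month 36 is 1 − (e^(−12λ) − e^(−36λ))/(24λ). This is 0.915 for a median of 6 and 0.793 for 9.84.
- 27 per arm: 24.7 + 21.4 = 46.1 events.
- 30 per arm, no loss: 27.5 + 23.8 = 51.2 events.

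**2. The plan's own figure, no look.** Power = Φ(ln(1.64)·√D/2 − 0.8416). For D = 46.1 this is Φ(1.680 − 0.842) = 79.9%. The other table rows, treated the same way, give 80.1% (HR 2.12), 80.3% (1.89) and 79.8% (1.74). All four rows therefore reproduce without an interim.

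**3. The stopping boundary.** Observed-trend conditional power is Φ((Z₁/√t − z_final)/√(1−t)). Setting it to 0.30 at t = 0.5 with z_final = 0.8416:

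Z₁ = √0.5 × (0.8416 − √0.5 × 0.5244) = 0.333.

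With 23.05 interim events, the hazard ratio at the boundary is exp(2 × 0.333/√23.05) = 1.15. The trial stops even when CC-486 is modestly ahead.

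**4. Power with the rule.** This is P(Z₁ > 0.333 and Z₂ > 0.8416), bivariate normal with correlation √0.5, final drift ln(1.64)·√D/2 and interim drift √0.5 times that.

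| Against one-sided 0.20 | Stop at HR 1.64 | Power, no look | Power with rule |
|---|---|---|---|
| 46.1 events | 19.6% | 79.9% | 71.6% |
| 51.2 events (no loss) | 17.9% | 82.3% | 74.2% |

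Of the 19.6%, 8.3 points (79.9 − 71.6) are lost successes; the other 11.3 would have failed the final test anyway. Under no effect, 63% stop and one-sided type I error is 0.160. Even if all 60 patients had events, power with the rule would be 78.2%.

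**5. Log-rank simulation, 20,000 trials each.**
- 54 evaluable, look at 23 events: 20.2% stopped, power 70.8%.
- 60 patients with random dropout of about 10% (47.3 events), look at 24: 20.7% stopped, power 70.6%.
- 60 patients, no loss, look at 26: 18.4% stopped, power 74.0%.

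A separate simulation of 10,000 trials per scenario gave 70.1–73.0% power with 10% loss and 74.2% with none.

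**6. If the final test is p < 0.05 (46.1 events).**

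| Final test | Stop at interim HR of or below | Stop at HR 1.64 | Stop, no effect | Power, no look | Power with rule |
|---|---|---|---|---|---|
| One-sided 0.05 (z = 1.645, Z₁ = 0.901) | 1.46 | 39% | 82% | 51% | 43% |
| Two-sided 0.05 (z = 1.960, Z₁ = 1.124) | 1.60 | 47% | 87% | 39% | 32% |

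**The case against.** The best defence is that this is a gap in reporting and not a failed design. Section 11.3.4 gives a fixed-design power that is correct on its own terms. Section 11.3.6 explains its choice, and a futility-only look lowers type I error. The loss is about 8 points in a small phase II trial sized by feasibility. That limits the remedy to a few sentences. It does not rescue the 80%, because a rule that will be followed is part of the design. Section 11.3.6 also argues that continuing is cheap and that the bar for doing so was set low; stopping about one trial in five at the design effect fits poorly with that aim.

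Three narrower objections have some force:
- **Range.** The 74% end was computed with no loss, which is not what 11.3.4 assumes. However, lighter dropout models leave 49–50 events and give 73.1–73.6%, so 71–74% is still fair. The simulated stopping probabilities with loss run slightly above 20%.
- **Expected progressions.** Section 11.3.6 does not say under which hypothesis they are counted. With both medians at 6 months, the same inputs give about 49 events (54 evaluable) or 55 (60 patients). A look at half of 49 changes power only to about 72.3%.
- **Significance level.** The conflict between 0.20 and 0.05 exists without any interim, and most of the power drop at 0.05 (to 51% or 39%) precedes the look. One-sided 0.20 is the more natural reading, since 11.3.6 refers back to the planning medians. The conflict still belongs here because conditional power cannot be calculated without a final critical value.

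The result also depends on the observed-trend scenario. Under the alternative scenario the same 30% cut-off would cost less than one point (79.0% at 46 events), but 11.3.6 does not use that scenario for the decision.

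**Conclusion.** The concern holds. Followed as written, the design has about 72% power (71–74%), not 80%, so the type II error is about 28% instead of 20%. The figure assumes exponential PFS, uniform accrual, a look at exactly half the events and a one-sided 0.20 final test. No treatment of the 10% loss restores 80%. The error is conservative for false positives. The unnamed final test matters more than the missing 8 points: it moves the stopping probability at the design effect from about 20% to 39% or 47%. This should be corrected, but it does not undermine the trial.

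**What to change.** - **11.3.6:** name the final test against which conditional power is computed; one-sided 0.20 matches the planning basis. State the expected number of progressions and the hypothesis it assumes (46 under the alternative with 54 evaluable patients, 51 with no loss). Report the stopping probabilities: about 20% at HR 1.64 (18–21% across loss models and simulation) and 63% under no effect.
- **11.3.4:** restate power as about 72% (71–74%) with the futility rule included, and note that one-sided type I error becomes about 0.16.
- **11.3.1:** say which significance level applies to the primary PFS comparison and which analyses the p < 0.05 criterion covers. If it is meant for PFS, report the 0.05 stopping and power figures instead.

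The cost is a few sentences and a less favourable power figure. No patients, visits or data are added, and neither the 30% cut-off nor the final critical value changes. The figures use only planning inputs, so they can be added even if the look has already taken place.

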12.1 Institutional Review Board/Ethics Committee approval

The protocol for this study has been designed in accordance with the general ethical principles outlined in the Declaration of Helsinki. The review of this protocol by the IRB/EC and the performance of all aspects of the study, including the methods used for obtaining informed consent, must also be in accordance with principles enunciated in the declaration, as well as ICH Guidelines, Title 21 of the Code of Federal Regulations (CFR), Part 50 Protection of Human Subjects and Part 56 Institutional Review Boards.

The Investigator will be responsible for preparing documents for submission to the relevant IRB/EC and obtaining written approval for this study. The approval will be obtained prior to the initiation of the study.

The approval for both the protocol and informed consent must specify the date of approval, protocol number and version, or amendment number. Any amendments to the protocol after receipt of IRB/EC approval must be submitted by the Investigator to the IRB/EC for approval. The Investigator is also responsible for notifying the IRB/EC of any serious deviations from the protocol, or anything else that may involve added risk to subjects.

Any advertisements used to recruit subjects for the study must be reviewed and approved by the IRB/EC prior to use.

